5.0 Study Intervention/Investigational Agent

5.1 Description:

The hardware of the VICT program consists of a fully-immersive High Tech Computer (HTC) VIVE™ VR viewer (OLED display with 2160×1200 resolution, 90Hz refresh rate, and 110 degrees of field of view) powered by a high-performance laptop (Dell Alienware™ 17), a pair of surround sound headphones reworked to integrate with the VR viewer, and a wireless one-hand controller for the child to interact with the virtual environment using gestures. Furthermore, to avoid the burden of the equipment's weight on a child's head, we created a special mechanical arm to suspend the VR viewer in front of a child's eyes with adjustable headphone positions. With the system securely fixed on a wheeled workstation, a child can operate the program by reclining on the bed/wheelchair in his/her own patient room. To ensure the hygiene, each child will use a new facial pad for the viewer and a pair of new earphone covers. All parts of the equipment will be sanitized with germicidal wipes after each use.

For the software, the Windows 10-based VICT program invites children to rescue an animated character named "Lubdub" from a castle. The program consists of three challenging and child-friendly tasks that correspond to the three core EFs. During the game, children need to (1) direct a group of sentinels away from the castle gates (VR Task #1, adapted from the Spatial Stroop Task to train Inhibitory

Control), (2) successfully open a series of castle gates by replicating the cryptography sequence of items surrounding each gate in forward/backward order (VR Task #2, adapted from the Visual Working Memory Task to train Working Memory), and finally (3) rescue Lubdub inside the castle by strategically matching patterns between the Lubdub and the four surrounding guards (VR Task #3, adapted from the Wisconsin Card Sorting Task to train Cognitive Flexibility). A tutorial mode preceding the training lets children learn how to interact with VR. In the training mode, children will complete each task starting at the easiest level and gradually moving to more difficult levels as easier levels are mastered. Each training session consists of 10-30 trials per task, taking about 15 minutes in total. Children will receive visual/audio feedback to learn and optimize their performance.

6.0 Procedures Involved*

The procedure involved for the study is described in detail below:

1) Baseline assessment. All approximately 30 children will complete the NIH Toolbox Cognition Battery tests, CPT 3, Virtual Reality Assessment, and the TBI-QOL Short Form prior to the randomization sequence. Both the assessor and the child will be unaware of group assignment at this point. Additionally, data regarding baseline measurement including proportion of planned baseline measures that are completed and the duration of each assessment will be documented.

2) Intervention. Following the baseline assessment, the approximately 30 children will be randomly assigned to one of the following two groups: intervention group (VICT training) or control group (a comparable VR game without cognitive training). The random allocation sequence will be generated using a SAS-based randomization program with 1:1 allocation ratio and random block sizes of 2 and 4. Both groups will first be provided a tutorial to be familiar with the VR environment. The length of time for either intervention game will be a minimum of 15 minutes of total play. If they are in the hospital, they will play approximately 15 minutes per day during their stay. If they have already been discharged from the hospital, the length of time is a minimum of 15 minutes of total play but can be more spread across their choice of days. Trained researchers who generate the randomization sequence and implement the VR will not participate in any subsequent outcome assessment. Note that although the length of training will vary across children depending on their length of stay or if they have been discharged, this arrangement has unique advantages over a fixed length of training in that: a) it provides consistency with standard therapies children are scheduled to receive, ensuring intervention to meet children's medical needs; and b) it ensures consistent timing and sufficient retention rates for future assessment.

Additionally, AEs and SAEs will be monitored in real-time throughout the intervention. Quantitative user feedback such as sickness, fatigue, and time estimates will be measured at the end of both the first and the last VR session. The

PROTOCOL TITLE: Virtual Reality-based Rehabilitation for Children with Traumatic Brain Injuries

semi-structured interview from the User Feedback Survey will also be conducted at the first and last VR session on children's perceived VR experience, benefits, and challenges.

3) Post-intervention assessment. At completion of intervention, all children will again complete the NIH toolbox Cognition Battery tests, the Conners CPT 3, the Virtual Reality Assessment, and the TBI-QOL Short Form with trained staff blinded to the intervention assignment. Data regarding post-intervention measurement including proportion of planned post-intervention measures that are completed and duration of each assessment will also be documented.

4) Follow-up assessment. All children will complete a follow-up assessment within approximately 6 months after intervention completion. Clinically, this gives the child and family a long enough time to identify cognitive and behavioral problems. Research staff blinded to group assignment will administer the NIH Toolbox tests, the Conners CPT 3, the Virtual Reality Assessment, and the TBI-QOL Short Form to children at this visit. Children will complete the child-PedsQL Generic Core Scales and their parents or legal guardians/representatives will complete the BRIEF2, CBCL-APS, and parent-PedsQL. Data regarding follow-up measurement including proportion of planned follow-up measures that are completed and duration of each assessment will be documented. Data regarding recruitment including number of children screened per month; number of children enrolled per month; proportion of eligible children who enroll, and treatment-specific retention rates will be documented throughout the study and aggregated at this stage.

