3.3 Provide the scientific or scholarly background for, rationale for, and significance of the research based on the existing literature and how will it add to existing knowledge.

Virtual reality (VR) offers an exciting alternative EF rehabilitation strategy for three reasons. First, VR technology has the capability to offer a multitude of activities for training children with TBI in core EFs⁸ within a versatile virtual environment. Such an enriched, immersive environment has already been shown effective in promoting structural and functional recovery of the human brain.²¹ Furthermore, because all VR-based EF training occurs within a safely controlled, automated virtual environment, it takes minimal physical space and personnel resources to implement in a medical setting, reducing expenses for both the hospitals and the families. Second, VR-based EF training can be readily provided via Internet and mobile platforms. This allows EF training, especially those sessions scheduled after discharge, to be completed without requiring children to leave home. Last but not least, unlike traditional computer-based EF training, we expect VR-based EF training to exert two positive effects on children's rehabilitation²²: (1) improved adherence. VR-based EF training was found especially appealing to pediatric patients in our pilot testing, possibly due to the youth population's increasing exposure to electronic games in recent years; (2) potentially better skill transfer to real life. Although research suggests mixed results of computerized training for cognitive skills in general, we expect VR training to translate trained skills into daily EF skills and overall QoL in pediatric TBI patients because (1) EFs are domain-general cognitive skills that can be gained in one setting and transferred to another;²³ (2) studies using representative national samples of children have supported EF as domain-general skills and documented positive relations between EFs and real-life outcomes,²⁴ and (3) Our pilot test of the VICT program on two pediatric patients with TBI at NCH showed positive changes of core EF scores after intervention (although this preliminary result should be interpreted with caution given that the changes could reflect other factors, such as natural recovery).

The overall goal of the proposed research is to evaluate the feasibility, safety, and efficacy of a VR-based interactive cognitive training (VICT) program in children 7-17 years with complicated mild to

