10.0 Inclusion and Exclusion Criteria*

10.1 Describe how individuals will be screened for eligibility.

Using electronic medical records and working with medical colleagues located in the hospital, trained research staff will identify potential participants admitted to NCH with a complicated mild, moderate, or severe TBI. Once identified as eligible to participate, research staff will approach legal guardians and eligible children on the hospital unit to introduce the research project. Staff will ensure children are awake, alert, and able to sign the assent form (if ≥ 9 years) and demonstrate understanding of the study before being approached for consent. In addition, a trauma registry request will be performed monthly to identify TBI patients discharged within the last 3 months. These patients, if eligible, will be mailed a study invitation, followed by an introduction phone call. Additional recruitment of discharged patients will be performed at follow up appointments using study flyers. Patients may also self-refer from the public domain through postings on sites such as clinicaltrials.gov (NCT03611062) and via IRB approved recruitment emails. Discharged patients will be offered the opportunity to

return to the hospital to receive the training. Consent and assent will be obtained at an in-person meeting. All TBI patients will be tracked using a Patient Reminder List in Epic.

10.2 Describe the criteria that define who will be included or excluded in your final study sample.

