12.0 Local Number of Subjects

12.1 Indicate the total number of subjects to be accrued locally.

The study will recruit approximately 30 children with complicated mild, moderate, or severe TBI at Nationwide Children's Hospital.

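### Care status at enrolment (in hospital or discharged) shapes training schedule and test interval, but it is neither a stratification factor nor a covariate in the efficacy models; adding it to 17.1 is a cheap gain

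*Combined protocol and SAP*

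**What the plan says.** All references are to the combined protocol and SAP.

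- **Size.** Section 12.0: "The study will recruit approximately 30 children with complicated mild, moderate, or severe TBI". With 1:1 allocation this is about 15 per arm.
- **Allocation.** Section 6.0, item 2, uses a "SAS-based randomization program with 1:1 allocation ratio and random block sizes of 2 and 4". No stratification factor is named there or elsewhere.
- **Schedule by care status.** The same item says of inpatients: "If they are in the hospital, they will play approximately 15 minutes per day during their stay". For discharged children, "the length of time is a minimum of 15 minutes of total play but can be more spread across their choice of days". It acknowledges that "the length of training will vary across children depending on their length of stay or if they have been discharged".
- **Test timing.** Section 6.0, item 3, places the post-intervention tests at the end of training, so the interval from baseline follows the training schedule.
- **Sources of children.** Besides inpatients, section 10.1 provides that "a trauma registry request will be performed monthly to identify TBI patients discharged within the last 3 months". It also uses flyers at follow-up appointments, recruitment emails and self-referral: "Patients may also self-refer from the public domain through postings on sites such as" a trial register. The criteria in 10.2 set no limit on time since injury.
- **Natural recovery.** Section 3.3 cautions about its two pilot patients that "the changes could reflect other factors, such as natural recovery".
- **Analysis.** Section 17.1 compares change in the NIH Toolbox composite, TBI-QOL and CPT 3 by ANCOVA with baseline score as the only covariate. It then regresses post-intervention Toolbox score on hours of VICT training, with controls set to zero.
- **Control variables elsewhere.** Section 27.0 (Confidential Health Information, item 2.0) says age, gender, race, GCS, Rancho level, therapy time and neuropsychological results will serve as control variables. Section 17.1 puts none of them in a model apart from baseline scores. Neither care status nor time since injury is on that list.

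**The concern.** The trial pools children who are still in hospital with children who went home weeks or months earlier. The two groups train on different schedules, are retested after different intervals, and are probably at different points of recovery. The protocol itself names recovery as a rival explanation for change.

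Baseline-score ANCOVA removes differences in starting level. It does not remove differences in recovery slope or in the length of the interval: two children with the same baseline score can have different expected change if one is an acute inpatient and the other has long been home. If one arm happens to receive more inpatients, part of the observed arm difference is then recovery, and no term in 17.1 separates the two. What is at stake is the preliminary effect size (Cohen's d), which is likely to inform planning of a later study.

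The dose regression is exposed in a further way. Within the VICT arm, hours of training depend on care status by design, and hours are not randomised, so the dose slope there can partly reflect status.

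**Working it through.** **The plan's own figure.** There is no power, alpha or effect-size figure to reproduce. N = 30 rests on recruitment (section 3.2): 0.80 × 30 = 24 eligible children a year, or 24 × 1.5 = 36 in 18 months against 30 needed. That is consistent.

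**Inputs from the documents.** N about 30; 1:1; random blocks of 2 and 4; one list; baseline score as sole covariate.

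**Assumptions (not in the documents).** Number of inpatients k between 9 and 21 of 30, with k = 15 as the worked case. Extra mean gain of inpatients through recovery, g = 0.5 to 1.0 SD, where SD is that of change within a care-status group after baseline adjustment. Any part of g already explained by baseline score would make the shifts below smaller.

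**Step 1: chance of imbalance.** With 15 per arm, the number X of inpatients in one arm is hypergeometric, and the difference in inpatient share is |2X − k|/15. For k = 15:

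P(10 v 5 or worse) = 2 × [C(15,10)² + C(15,11)² + … + C(15,15)²] / C(30,15) = 2 × 11,099,510 / 155,117,520 = 0.143.

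Simulating the stated blocks (40,000 runs) gives 0.146. For other k, the exact values are:

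| Inpatients of 30 | P(share differs by ≥ 20 points) | P(≥ 33 points) |
|---|---|---|
| 9 or 21 | 0.43 | 0.11 |
| 12 or 18 | 0.26 | 0.06 |
| 15 | 0.47 | 0.14 |

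The values do not move smoothly because the count difference must be odd or even with k. For k = 10, the simulated chance of 7 v 3 or worse is 0.246.

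**Step 2: shift in the arm difference.** Shift = imbalance in share × g.

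- 10 v 5: 5/15 × 0.5 = 0.17 SD; 5/15 × 1.0 = 0.33 SD.
- 7 v 3: 4/15 × 0.5 = 0.13 SD; 4/15 × 1.0 = 0.27 SD.
- Typical (one-SD) imbalance of 0.17 to 0.19: 0.17 × 0.5 = 0.09 SD up to 0.19 × 1.0 = 0.19 SD.

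**Step 3: compare with sampling error.** SE = √(2/15) = 0.365 SD. The 10 v 5 shift is 0.46 to 0.91 of one SE.

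**Step 4: what a covariate does at 10 v 5.** The correlation of arm with status is (10 × 10 − 5 × 5)/(15 × 15) = 1/3. Including status removes the shift if its effect is additive. Variance inflation is 1/(1 − 1/9) = 1.125, so the SE rises by a factor √1.125 = 1.06.

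**Step 5: average over all allocations (k = 15).** The imbalance has SD 0.189 under the stated blocks, and the mean squared arm-status correlation is about 1/29.

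| SD of the estimated arm difference | g = 0.5 | g = 1.0 |
|---|---|---|
| As planned: √(2/15 + (0.189g)²) | 0.377 | 0.411 |
| Status in the model: √((2/15)(1 + 1/29)) | 0.371 | 0.371 |
| Status in the model and separate lists: about √(2/15) | 0.365 | 0.365 |

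Break-even is where (0.189g)² = (2/15)/29 = 0.0046, so g = 0.36. Below that gap the covariate costs slightly more precision than it returns, at most 0.371 against 0.365.

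**Step 6: separate lists.** In simulation with the same blocks run within each status, inpatient counts differed between arms by at most 2 (even k) or 1 (odd k). Total arm sizes differed by at most 4.

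**The case against.** The strongest reply is that nothing here is an error of randomisation. Chance imbalance is not bias: the estimate is right on average, and the spread that imbalance causes is already part of its sampling error. With 15 inpatients, about 85% of allocations are better balanced than 10 v 5, and even the largest shift quoted is below one standard error. The recovery gap has no source in the documents. Efficacy is the second endpoint (section 4.1), and section 2.2 says no hypotheses will be tested. Variable training length is a reasoned choice, partly made to explore dose (section 9.1). A model covariate captures most of the benefit, so stratified lists are largely a preference. All of this stands, and it limits the point to a modest improvement.

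Two further replies stand in part. Care status is an imperfect stand-in for recovery phase: the discharged group would pool a child home for a week with one home for many months, and the inpatient group mixes units and severities. That is a reason to record date of injury as well, not to leave status out. Also, section 27.0 shows that confounding was considered. But 17.1 does not use that list apart from baseline scores, and the list omits both status and time since injury.

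A reader might infer that the efficacy result will be driven by which arm gets the acute patients, that the allocation scheme is invalid without stratification, or that status fixes recovery phase. The documents support none of these. They give neither the inpatient share nor the recovery gap, a 1:1 blocked list is valid, and the link from status to recovery phase is an inference.

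**Conclusion.** The point holds as a low-cost improvement to the analysis plan. By the protocol's own text, care status determines the training schedule and so influences the test interval; it is known before allocation, yet it enters neither the allocation nor any efficacy model. At about 15 per arm, a gap of at least 20 points in inpatient share has a 26% to 47% chance for the inpatient counts tabulated (9 to 21 of 30). A 10 v 5 split would move the exploratory effect size by 0.17 to 0.33 SD, against a standard error of about 0.37 SD.

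This rests on two assumptions, the inpatient share and the 0.5 to 1.0 SD recovery gap. With a 1.0 SD gap, adjustment lowers the SD of the arm difference from 0.41 to 0.37; with 0.5 SD the average gain is slight (0.377 to 0.371), and the main benefit is protection in the particular allocation that occurs. The feasibility and safety endpoints are not the target of this point.

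**What to change.** 1. In 17.1, prespecify care status at enrolment (in hospital or already discharged) as a factor in the ANCOVA comparisons and in the dose regression.
2. Reconcile 17.1 with section 27.0, Confidential Health Information, item 2.0: state which of the control variables listed there enter which model, or drop the statement that they will. With about 30 children only a few can be carried.
3. Add date of injury to the data list in 17.4, so that time since injury can be a sensitivity covariate. Section 27.0 offers date categories such as admission and discharge, but date of injury is not among the items named.
4. Optional, for children not yet randomised: generate one list per care status in section 6.0, item 2, with the same SAS program and block sizes.

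Cost: one model factor (one residual degree of freedom) and one data field. In a 10 v 5 allocation the factor adds about 6% to the standard error while removing the shift. Separate lists need one extra list and can leave total arm sizes up to 4 apart.

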4.0 Study Endpoints

4.1 Describe the primary and secondary study endpoints.

The primary study endpoint is the protocol feasibility (defined as protocol completion rate and subjective VR experience ratings) and safety (see section 4.2) of the VICT program. The second study endpoint is the preliminary efficacy of the VICT program, defined as the changes in NIH Toolbox Composite Scores before and after the intervention.

4.2 Describe any primary or secondary safety endpoints.

The primary safety endpoint is the number of adverse events. The secondary endpoint is the scores on participants' simulator sickness and exertion.

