15.0 Risks to Subjects*

We believe that there is minimal risk for being in this study.

It is possible that the subject might feel motion sickness using the virtual reality goggle. They might also experience other virtual reality side effects, which can include but are not limited to, blurry vision, eye strain, headaches, dizziness, fatigue, or nausea. The subject has the right to terminate using the virtual reality goggle any time during the study if there is any discomfort arising from using the virtual reality goggle. The risk of motion sickness will be minimized by allowing subjects to terminate use of the VR intervention at any time during the study.

Although we will take every precaution including secure data storage on password-protected computers and REDCap, there is a small chance of loss of confidentiality of study information. The risks related to patient confidentiality will be minimized by creating a separate link file for patient study ID and the MRN. The study ID will be used on the questionnaires. Patients' medical data will be reviewed and abstracted by trained researchers. All data will be stored on a secure server at NCH. The Patient ID-Participant ID link file will be stored in a separate location on the server from other study data for an additional layer of security and confidentiality.

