17.0 Data Management* and Confidentiality

17.1 Describe the data analysis plan, including any statistical procedures or power analysis.

To examine the research paradigm (Aim 1), we will compute average number of children screened and enrolled per month, proportion of eligible children who enroll, treatment-specific retention rates, proportion of children who adhere to assigned condition, proportion of planned measures that are completed, and average duration of completing each measurement. To examine the feasibility and safety of the VICT program (Aim 2), the total number of AEs/SAEs, mean simulator sickness scores, and mean Borg exertion scores will be computed and compared between the intervention and control group using independent samples t-tests. Additionally, open-end feedback from children, parents, and clinicians on optimizing the VR games and best practices in protocol implementation will be synthesized and submitted to the VR development team for improvement. Finally, to explore the preliminary efficacy of the VICT program (Aim 2), difference scores from baseline to post-intervention and baseline to follow-up of the composite NIH Toolbox score, TBI-QOL, and Conners CPT 3 will be compared between the intervention group and the control group using analysis of covariance (ANCOVA) controlling for baseline scores. BRIEF2, CBCL-APS, and PedsQL (parent/child) scores at follow-up will be compared between the two groups using ANCOVA controlling for baseline scores. Cohen's d for core EFs changes will be computed as the preliminary intervention effect size. Finally, dosage effect will be evaluated within regression analyses, with dosage (0 for controls, cumulative hours of VICT training for intervention group) as the primary predictor and post-intervention NIH Toolbox scores as the outcome variable.

17.2 Describe the steps that will be taken to secure the data (e.g., training, authorization of access, password protection, encryption, physical controls, certificates of confidentiality, and separation of identifiers and data) during storage, use, and transmission.

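### Simulator sickness and exertion, the secondary safety endpoint, are scored only after VR and compared between two VR arms, so these scores cannot separate a VR effect from symptoms already present

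*Combined protocol and SAP*

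**What the plan says.** Section 4.1 makes the feasibility and safety of the VICT program the primary study endpoint. Section 4.2 ranks the safety measures: "The primary safety endpoint is the number of adverse events". Then: "The secondary endpoint is the scores on participants' simulator sickness and exertion".

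Section 6.0, item 2, fixes when the symptom ratings are taken: "sickness, fatigue, and time estimates will be measured at the end of both the first and the last VR session". The baseline list in item 1 consists of the NIH Toolbox battery and "CPT 3, Virtual Reality Assessment, and the TBI-QOL Short Form prior to the randomization sequence". No sickness or exertion rating is named there or at any other time before VR.

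The comparator is described in item 2 as "control group (a comparable VR game without cognitive training". The same item adds: "Both groups will first be provided a tutorial to be familiar with the VR environment".

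For the analysis, Section 17.1 takes the AE/SAE totals and the mean sickness and Borg exertion scores, to be "compared between the intervention and control group using independent samples t-tests". It does not say whether the first-session or last-session score is meant. The same section uses baseline-adjusted change for the NIH Toolbox, TBI-QOL and CPT 3, but not for sickness or exertion.

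Section 15.0 lists the expected VR side effects, among them "blurry vision, eye strain, headaches, dizziness, fatigue, or nausea".

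**The concern.** Section 3.3 describes VICT as hardware and software together, and Section 15.0 attributes the expected symptoms to VR. A reader will therefore want these scores to show how much symptom burden the headset sessions bring. The planned analysis gives two numbers, and neither does this.

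- **The between-arm difference.** Both arms wear the headset, so symptoms that VR causes equally in both do not appear in it.
- **The post-session mean.** These children have complicated mild to severe TBI and may already have headache, dizziness, fatigue or nausea. Without a score before VR, the mean mixes injury and VR.

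A null difference could then be reported beside a substantial VR effect, and a high mean could be blamed on VR when it comes from the injury. The plan gives no reference value or acceptable level against which to read the mean.

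**Working it through.** The plan states no alpha, power, effect size or SD for this comparison, so there is no figure to reproduce. The check is of what the planned contrast estimates.

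**Inputs from the document.** About 30 children (Section 12.1) and 1:1 allocation (Section 6.0), so 30 / 2 = 15 per arm. Scores are taken after VR only, and both arms use VR.

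**Assumed inputs.** Two-sided alpha 0.05, 80% power, score SD 1, and a within-child correlation r between pre and post scores of 0.5 (range 0.3 to 0.7). Exertion is assumed to be collected with the sickness rating, because Section 6.0 does not time it separately.

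**Step 1: what each quantity estimates.** Let b be the mean symptom level already present, v the rise due to VR in either arm, and c the extra rise due to VICT content.

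- Control mean after VR: b + v
- VICT mean after VR: b + v + c
- Planned contrast: (b + v + c) − (b + v) = c

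So v drops out of the contrast, and the means give only the sum b + v. The change from first to last session does not recover v either, because both scores follow VR and recovery between them is mixed in.

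**Step 2: the planned t-test when VR affects both arms equally (c = 0).** There were 20,000 simulated trials with 15 per arm. The last column is a paired pre-post test in all 30 children at r = 0.5.

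| Rise due to VR, both arms | Planned t-test rejects | Paired test rejects |
|---|---|---|
| 0 SD | 5.0% | 4.8% |
| 0.5 SD | 5.1% | 75% |
| 1 SD | 4.7% | over 99% |
| 2 SD | 4.8% | 100% |

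The simulation error of a 5% rate is √(0.05 × 0.95 / 20,000) = 0.15 percentage points, so the planned-test column does not depart from 5% beyond chance. This follows from the design: the test rejects at its alpha level whatever the value of v.

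**Step 3: the question the t-test does answer (c).** With 15 per arm, 80% power needs a difference of d = 1.06 SD (noncentral t). By the normal approximation, power = Φ(d√(15/2) − 1.96):

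- d = 0.5: Φ(1.37 − 1.96) = Φ(−0.59) = 28%
- d = 0.8: Φ(2.19 − 1.96) = Φ(0.23) = 59%

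So a non-significant result is weak evidence even about content-specific symptoms.

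**Step 4: the paired alternative.** With 30 pairs, 80% power is reached at a standardized change dz (mean change divided by the SD of the changes) of 0.53. In units of the score SD this is 0.529 × √(2(1 − r)):

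- r = 0.3: 0.63
- r = 0.5: 0.53
- r = 0.7: 0.41

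With 24 complete pairs dz is 0.60, and within one arm of 15 it is 0.78.

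**The case against.** The strongest reply is that safety here does not rest on these scores. Adverse events are the primary safety endpoint and are monitored in real time (Section 6.0). Section 14.0 sets an absolute 20% limit on SAEs attributed to the study. Children are interviewed about their VR experience and its challenges at the first and last sessions. A reader might infer that the trial's safety assessment as a whole can say nothing about VR; the documents do not support that. What stands against the reply is narrower: no assessment of AE causality or analysis by relatedness is described, so these sources do not make the sickness and exertion scores interpretable.

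The study is also declared exploratory with no hypotheses (Section 2.2). Whether VICT content adds symptoms over a comparable game is a legitimate question, and the t-test addresses it. Both points stand. Nothing in the plan says that a null result will be reported as proof of safety; that is a possible misreading, not a stated intention.

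A reader might further infer that last-session scores come mainly from children who tolerated VR, since anyone may stop for discomfort (Sections 14.0 and 15.0). The documents do not establish this. Total play may be as short as 15 minutes (Section 6.0) and a session takes about 15 minutes (Section 5.1), so for some children the first and last session may be the same. For a child who stops, the session at which they stop may count as the last, and nothing says that the rating is then skipped. No size can be put on such selection from the documents.

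Finally, the content of the baseline Virtual Reality Assessment is not defined, and Section 6.0 gives its ratings as examples. A symptom score before VR may exist in material not included here, but nothing in the plan says so.

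**Conclusion.** The point holds for simulator sickness and exertion. As planned, their between-arm comparison estimates only the added effect of VICT content. It is blind to a symptom effect common to both VR arms: rejection stays at about 5% for shared rises from 0 to 2 SD. The arm means describe symptom levels after VR but cannot be divided between VR and injury.

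The cancellation depends only on both arms using VR, which the plan states. The 5% rests on an assumed alpha, and the paired-analysis figures rest on the assumed alpha, power and correlation. The conclusion about the means assumes that no symptom rating before VR is hidden in the Virtual Reality Assessment.

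It might be inferred that adding a pre-session score would prove that VR causes symptoms. It would not: without a non-VR control, other influences remain, such as fatigue from assessment visits of about 60 minutes (Section 9.1). Attribution to VR would be supported, not proven.

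This is an inexpensive improvement to a secondary safety measure and should be made. It does not invalidate the trial.

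**What to change.** **Section 6.0.** Give the same sickness and exertion items once before any VR exposure: before the tutorial, and before the baseline Virtual Reality Assessment if that uses the headset. If the first VR session falls on a different day, give them again just before it. State what the Virtual Reality Assessment contains.

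**Section 17.1.**
- Make the main estimate for these scores the within-child change (end of first session minus pre-session), pooled over arms and by arm, with 95% CIs.
- Keep the between-arm difference as secondary, and state that a non-significant difference is not evidence that VR is safe.
- Report last-session scores with the number of children who stopped early, using the score at stopping where available.

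**Cost.** One more administration of a rating already in use, or two if the first session is on another day, at an assumed 1 to 2 minutes each, plus a few lines of text. No extra visit or staff is needed.
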